Efficacy of Kinesio Taping in Musculoskeletal Neck Pain in Short and Medium Term. A Randomized Control Double Blinded Clinical Trial

TITLE: Efficacy of Kinesio Taping in Musculoskeletal Neck Pain in Short and Medium Term. A Randomized Control Double Blinded Clinical Trial

INVESTIGATOR PRINCIPAL: [name]

PROJECT ENTITIES: COMPLUTENSE UNIVERSITY OF MADRID & NURSERY, PHYSIOTHERAPY AND PODIATRY FACULTY.

NUMBER OF IDENTIFICATION:

DATE: 1ST JUNE 2021.

STUDY PROTOCOL

Type of Study: A double-blind controlled clinical trial was conducted with 30 days following.

Target population: Population with musculoskeletal neck pain.

Sample: A convenience sampling will be carried out among the patients according to eligibility criteria.

Inclusion criteria:

- Age between 18 and 30 years old,
- Presence of myofascial pain syndrome (MPS) and myofascial trigger point (MTP) in the upper trapezius muscle, according to the diagnostic criteria proposed by the American Academy of Pain Medicine and the scientific community a) tender point on palpation, with or without referred pain b) patient recognizes pain during tender point palpation c) at least three of the following: muscle stiffness or muscle spasm, limited range of motion in an associated joint, increase of pain with stress, palpation of tight band and / or nodule, associated with a tender point

- Understand written Spanish.

Exclusion Criteria:

- Neck pain of traumatic origin, due to recent surgery or causing radiculopathy.
- Have been diagnosed with chronic pathology, as well as neoplastic or suspicion of it.
- Have received some type of pharmacological or non-pharmacological analgesic treatment in the last 30 days
- Pregnant or menstrual women.

Sample size

The required sample size was calculated using the G * Power software (G * Power version 3.1.9.6). To identify the differences between the 3 intervention groups at the 3 evaluation moments, the sample size was estimated based on finding a moderate effect size (Cohen's $f = 0.25$). Considering an alpha error of 5% (0.05) and a beta error of 10% (statistical power of 0.9), he estimated the need for a sample size of at least 45 patients in total.

Procedure

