During the months of May to July 2021, a research assistant will contact potential participants who will be invited to participate in this study. Once they agree to participate, it will schedule for a face-to-face consultation at the university, where the main researcher will inform the study participants. Once the information sheet and informed consent will be a sign, an investigator will carry out the

measurements of the variables for initial data collection in the first session. In another room, an expertise physiotherapist with experience in applying Kinesio taping will perform interventions on patients on the same day as the initial evaluation. In this way, the investigator that will assess outcomes will be blind to the treatment that each patient will receive.

At the second consultation, 4 days after the first, the same physiotherapist who applied the bandage will remove it from the patients who will receive it and any remains of the bandage on the skin were cleaned. For patients in the control group (nothing apply), it will be the same protocol to alter not the double-blind. The principal investigator will perform the evaluations and data collection without knowing the intervention the patient will receive. In a third consultation, as a follow-up (30 days after the second consultation), the collection of the same measurements and clinical variables from the patients who completed the process will repeat by the same investigator that did the outcomes' assessment.

The information sheet, the informed consent, and the evaluation instruments will be collected by a researcher, stored, and guarded in the Department of Radiology, Rehabilitation and Physiotherapy of the Complutense University of Madrid. Thus, complying with the provisions of Organic Law 3/2018, of December 5, on the Protection of Personal Data and guarantee of digital rights.

Ethical Aspects

The study has the approval of the research commission of the Faculty of Nursing, Physiotherapy and Podiatry of the Complutense University of Madrid. Also, with the favorable opinion of the research commission of the Hospital Clinico San Carlos, Madrid. Lastly, it will be evaluated by the Ethics Committee of the research institute Hospital Clinico San Carlo Madrid, Instituto de investigación Sanitaria Hospital Clínico San Carlos (IdISSC).

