Efficacy of Kinesio Taping in Musculoskeletal Neck Pain in Short and Medium Term. A Randomized Control Double Blinded Clinical Trial

TITLE: Efficacy of Kinesio Taping in Musculoskeletal Neck Pain in Short and Medium Term. A Randomized Control Double Blinded Clinical Trial

INVESTIGATOR PRINCIPAL: [name]

PROJECT ENTITIES: COMPLUTENSE UNIVERSITY OF MADRID & NURSERY, PHYSIOTHERAPY AND PODIATRY FACULTY.

NUMBER OF IDENTIFICATION:

DATE: 1ST JUNE 2021.

Statistical Analysis Plan

The statistical software IBM SPSS® (Statistical Package for the Social Sciences 22, SPSS Inc., Chicago, IL USA) was used. The quantitative variables were presented as mean \pm standard deviation (SD), while the qualitative variables were shown as an absolute value (relative frequency percentage). To study the effects produced on the main variables of each intervention at different times of evaluation, an analysis of variance of repeated measures (factorial ANOVA) was applied. Secondarily, the same analysis was performed for each intervention on the secondary variable.

Additionally, the effect size (partial eta squared, η^2) was calculated for the changes produced by comparing within the same intervention group (intragroup) and comparing between intervention groups (intergroup), following the classification criteria described by Cohen: small (0.1 - 0.24), moderate (0.25 - 0.39), and large (> 0.4)

The interpretation of the statistical tests was performed based on a significance level of 5% ($p < 0.05$) for a 95% confidence interval.

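### In its usual SPSS form, the planned repeated-measures ANOVA drops the day-4 data of any patient who has no visit-3 value

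*Protocol*

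**What the plan says.** **Protocol, title.** The trial is about "Efficacy of Kinesio Taping in Musculoskeletal Neck Pain in Short and Medium Term", so the early and the later result are both headline questions.

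**Protocol, Sample size.** The calculation is framed "To identify the differences between the 3 intervention groups at the 3 evaluation moments" and arrives at 45 patients. It mentions no allowance for loss.

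**Protocol, Procedure.** Patients are measured at the first visit and again "At the second consultation, 4 days after the first". A third visit follows 30 days later (day 34), for which the text says "the collection of the same measurements and clinical variables from the patients who completed the process will repeat by the same investigator". The process that has to be completed is not defined.

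**Protocol, Ethical Aspects.** Consent can be withdrawn at any time. Nothing is said about follow-up of patients who stop early, or about data already collected from them.

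**SAP.** The only method given for comparing the main variables over the evaluation times is that "an analysis of variance of repeated measures (factorial ANOVA) was applied". The software is SPSS 22, and the same method is repeated for the secondary variable. The SAP does not name the SPSS procedure, an analysis population, a rule for missing values, or a separate day-4 analysis.

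**The concern.** Classical repeated-measures ANOVA, as usually run in SPSS, needs every time point for every patient. A patient with baseline and day-4 values but no day-34 value is removed from the whole model, including its baseline-to-day-4 contrast. Whether an early result counts then depends on attendance a month later.

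Two things are at stake. The first is precision: day-4 values already in hand are not used in a trial of only 45 patients. The second is bias in the short-term estimate, if loss differs between arms and is related to how patients felt at day 4. The undefined completion condition adds to this because it can be read as leaving out of the third visit some patients who stopped early but could still be measured.

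**Working it through.** **Inputs from the documents:** 3 groups, 3 evaluations, f = 0.25, alpha 0.05, power 0.90, N = 45.

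**Assumed, because the documents do not give them:** 15 patients per arm, SD 1, equal correlation rho between visits, sphericity, no true effect in the bias scenarios, and every loss rate below.

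**1. The plan's own figure.** For the group-by-time test, lambda = f² × N × 3 / (1 − rho), with df 4 and 2(N − 3). At rho 0.5 and N = 45, lambda = 0.0625 × 45 × 3 / 0.5 = 16.875 with df 4 and 84, and power is 0.911. The smallest N reaching 0.90 is 44, or 45 with equal groups. The stated 45 is therefore reproduced, and it presumes 45 patients with all three measurements.

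**2. Power with fewer complete cases (secondary, because rho is unstated).**

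| rho | 45 | 40 | 36 |
|---|---|---|---|
| 0.4 | 0.846 | 0.792 | 0.739 |
| 0.5 | 0.911 | 0.868 | 0.823 |
| 0.6 | 0.963 | 0.938 | 0.906 |

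**3. Precision at day 4.** If k patients in every arm miss visit 3, deletion multiplies the standard error of the day-4 contrast by sqrt(15 / (15 − k)), whatever rho is. For k = 1, 2, 3 this is 1.035, 1.074, 1.118. At rho 0.5 the contrast of changes from baseline has standard error sqrt(2/15) = 0.365 SD with 15 per arm and sqrt(2/12) = 0.408 SD with 12 per arm. If all day-4 values are used there is no increase.

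**4. Shift in the change from baseline to day 4.** Loss is in one arm only and logistic in the day-4 score, with odds ratio 1.5 / 2 / 3 per SD worse (200,000 simulated arms). The completers of that arm look better by, in SD:

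| rho | 10% loss | 20% loss |
|---|---|---|
| 0.3 | 0.028 / 0.047 / 0.069 | 0.055 / 0.090 / 0.130 |
| 0.5 | 0.020 / 0.034 / 0.049 | 0.040 / 0.065 / 0.093 |
| 0.7 | 0.013 / 0.021 / 0.030 | 0.024 / 0.039 / 0.056 |

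These are shifts in the change from baseline, which is why they depend on rho. If the completers' day-4 mean moves by d, their baseline mean moves by rho × d and the change moves by (1 − rho) × d. Check for 20% loss and odds ratio 3: 0.130/0.7, 0.093/0.5 and 0.056/0.3 all give d of about 0.19. As an extreme, losing exactly the 1, 2 or 3 worst day-4 scorers of one arm gives 0.063, 0.116 or 0.165 SD at rho 0.5. With all day-4 values used, the shift is zero in every case.

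**5. Type I error of the group-by-time test** (rho 0.5, 20,000 runs each, Monte Carlo SE about 0.0016): 0.048 with no loss, 0.049 to 0.054 under the graded loss of step 4, and 0.054 / 0.059 / 0.066 in the extreme case.

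**6. Completers against a mixed model** (3 lost from one arm, rho 0.5, 20,000 runs, Monte Carlo SE 0.003), bias in SD:

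| Loss depends on | Contrast | Completers | Mixed model |
|---|---|---|---|
| day-4 score | day 4 | −0.161 | 0.003 |
| day-4 score | day 34 | −0.002 | −0.001 |
| day-34 score | day 4 | −0.006 | −0.005 |
| day-34 score | day 34 | −0.167 | −0.230 |

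A repeat simulation of the last row gave −0.16 against −0.22. The gain from the mixed model is at day 4. At day 34 it can do somewhat worse if loss depends on the unseen score.

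**The case against.** - **The wording about completion is not the main cause.** This stands. A patient who missed visit 2 has no day-4 value to discard. The figures above describe ordinary loss between day 4 and day 34, which could happen under any wording. The phrase may mean no more than those who attend, and the effect of rewording it has not been quantified.
- **Case deletion is not stated.** This is also correct: it follows from the usual behaviour of the named method. But the plan names no other method and no rule that would retain the day-4 values.
- **The effect is small.** This stands as well. At rho 0.5 the graded shifts are 0.020/0.365 to 0.093/0.365, about 5% to 25% of one standard error, and type I error hardly moves. Similar loss in all arms largely cancels the bias and leaves only the loss of precision.
- **A smaller remedy exists.** A prespecified baseline-to-day-4 comparison on all available values would also retain the data, so choosing a mixed model is partly preference. The argument for it is that one model, with one stated population, yields both the day-4 and the day-34 contrasts. Its reliance on missing at random, and its larger bias in the last row of step 6, are real costs.

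**Conclusion.** The point holds as an avoidable inefficiency with a possible modest bias, of minor to moderate severity. It rests on the method being run in its standard complete-case form and on some patients being measured at day 4 but not at day 34. The amount and pattern of loss are unknown, so all the sizes above are illustrations over assumed ranges.

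A reader might infer more, in three ways that the documents do not support:

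- **That the plan excludes non-completers by rule.** The Procedure leaves completion undefined, and the SAP sets no analysis population.
- **That the short-term result would be seriously biased or its test invalid.** Only the extreme scenario takes type I error as far as 0.066, and no loss figures are documented.
- **That 45 is a wrong sample size.** It reproduces under rho 0.5. The documents do not show how much loss to expect, so the shortfall in power cannot be fixed at one value.

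**What to change.** **SAP.** Make the main analysis a linear mixed model for repeated measures (SPSS MIXED). Include group, categorical time and their interaction, with unstructured covariance and baseline as one of the three measurements. Analyse by allocated group and use all available values. Report the day-4 and day-34 group contrasts from this model, and losses by arm and visit. Keep the completers ANOVA as a secondary analysis and show both sets of results. A sensitivity analysis at day 34 that makes the missing values progressively worse by a fixed amount is optional.

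**Procedure.** Replace the completion condition for the third visit with all allocated patients who have not withdrawn consent, for visits still to come.

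**Cost.** One sentence in the Procedure and a few in the SAP, in the software already named, plus slightly more analysis work and possibly some extra contacts with patients who stopped early. The main estimate then relies on missing at random, and the mixed model does not repair day 34 if loss depends on the day-34 score; that is why both analyses should be shown.

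**Timing.** The plan is dated 1 June 2021 and recruitment runs from May to July 2021. The Procedure change helps only visits not yet made; the SAP change can be applied to data already collected.

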Efficacy of Kinesio Taping in Musculoskeletal Neck Pain in Short and Medium Term. A Randomized Control Double Blinded Clinical Trial

TITLE: Efficacy of Kinesio Taping in Musculoskeletal Neck Pain in Short and Medium Term. A Randomized Control Double Blinded Clinical Trial

INVESTIGATOR PRINCIPAL: [name]

PROJECT ENTITIES: COMPLUTENSE UNIVERSITY OF MADRID & NURSERY, PHYSIOTHERAPY AND PODIATRY FACULTY.

NUMBER OF IDENTIFICATION:

DATE: 1ST JUNE 2021.

Statistical Analysis Plan

The statistical software IBM SPSS® (Statistical Package for the Social Sciences 22, SPSS Inc., Chicago, IL USA) was used. The quantitative variables were presented as mean \pm standard deviation (SD), while the qualitative variables were shown as an absolute value (relative frequency percentage). To study the effects produced on the main variables of each intervention at different times of evaluation, an analysis of variance of repeated measures (factorial ANOVA) was applied. Secondarily, the same analysis was performed for each intervention on the secondary variable.

Additionally, the effect size (partial eta squared, η^2) was calculated for the changes produced by comparing within the same intervention group (intragroup) and comparing between intervention groups (intergroup), following the classification criteria described by Cohen: small (0.1 - 0.24), moderate (0.25 - 0.39), and large (> 0.4)

The interpretation of the statistical tests was performed based on a significance level of 5% ($p < 0.05$) for a 95% confidence interval.

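### The repeated-measures ANOVA appears to use the pre-treatment value as one of three response times; a baseline-adjusted mixed model of day 4 and day 34 would usually be more powerful and would keep partial follow-up

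*SAP*

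**What the plan says.** The SAP's stated purpose is to study "the effects produced on the main variables of each intervention at different times of evaluation", and for this "an analysis of variance of repeated measures (factorial ANOVA) was applied". It does not list the levels of time, say which term decides the result, name a baseline covariate, or say what happens when a visit is missing.

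The protocol supplies the times. Its Sample size section sets the aim: "To identify the differences between the 3 intervention groups at the 3 evaluation moments". Its Procedure section describes three assessments:

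- an initial one ("measurements of the variables for initial data collection in the first session"), after which a physiotherapist will "perform interventions on patients on the same day as the initial evaluation";
- one "At the second consultation, 4 days after the first";
- one "as a follow-up (30 days after the second consultation"), that is, day 34.

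The Sample size section gives "the need for a sample size of at least 45 patients in total" and no dropout allowance. The Procedure section limits the third assessment to patients who completed the process.

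**The concern.** Read together, the documents imply that the pre-treatment measurement enters the ANOVA as an outcome. Randomised treatment cannot affect that value. Its best use is to explain between-patient variation in the later values, which is what a baseline covariate does. In the group-by-time test the baseline instead acts much like the subtracted term of a change score, which carries its noise into the comparison.

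The baseline is collected anyway. With about 15 patients per arm (if allocation is equal), the unused information can be worth a good deal of power. Separately, a classical repeated-measures ANOVA normally drops a patient who lacks any one visit. This is a property of the method; the SAP does not state it. Day-4 data from patients lost before day 34 would then be discarded in a trial with no stated margin for loss.

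**Working it through.** **Inputs.** From the protocol's Sample size section: 3 groups, 3 times, Cohen's f = 0.25, alpha 0.05, power 0.90, N = 45. Assumed, because the documents do not give them: equal arms (3 × 15), the same correlation rho between all visits, and sphericity. The main variables are not named, so rho cannot be narrowed; 0.3 to 0.8 is shown.

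**Reproducing N = 45.** For the group-by-time interaction, λ = f²·N·3/(1 − rho), with df 4 and 2(N − 3). At rho 0.5, λ = 0.0625 × 45 × 3 / 0.5 = 16.875 with df 4 and 84, which gives power 0.911. N = 42 gives 0.887, so 45 is the smallest equal-arm total that reaches 0.90. Alternatives at the same rho do not give 45: time effect 36, between-group effect 141, two-time interaction 54, one-way ANOVA 207. This supports the reading that time has three levels, baseline included, and that the interaction is the intended term. For rho 0.3 / 0.5 / 0.7 / 0.8, power at N = 45 is 0.78 / 0.91 / 0.99 / 1.00.

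**What f = 0.25 means in SD units.** If one arm is shifted by d at both follow-ups, or at day 4 only, f² = (1/9)(2/3)(2/3)d² = (4/81)d², so d = 0.25 × 9/2 = 1.125 SD. If the shift halves by day 34, f² = d²/27, so d = 1.30 SD and then 0.65 SD.

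**Variance at one follow-up.** Per patient, a change score has variance 2(1 − rho)SD² and a baseline-adjusted value has (1 − rho²)SD². The ratio is (1 + rho)/2 = 0.65 / 0.75 / 0.85 / 0.90. This explains the mechanism; it is not a comparison with the pooled interaction test, so power is compared directly below.

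**Power with complete data, 3 × 15.** Planned interaction test v joint 4-df test of no group difference at day 4 or day 34, adjusted for baseline (simulated).

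| Effect in one arm | rho 0.3 | 0.5 | 0.7 | 0.8 |
|---|---|---|---|---|
| f = 0.25, both visits | 0.78 v 0.96 | 0.91 v 0.98 | 0.99 v 1.00 | 1.00 v 1.00 |
| f = 0.25, halved by day 34 | 0.78 v 0.94 | 0.91 v 0.97 | 0.99 v 1.00 | 1.00 v 1.00 |
| f = 0.25, day 4 only | 0.78 v 0.83 | 0.91 v 0.92 | 0.99 v 0.99 | 1.00 v 1.00 |
| 0.8 SD, both visits | 0.45 v 0.72 | 0.61 v 0.77 | 0.85 v 0.90 | 0.97 v 0.98 |
| 0.8 then 0.4 SD | 0.34 v 0.52 | 0.47 v 0.59 | 0.72 v 0.77 | 0.89 v 0.91 |
| 0.8 SD, day 4 only | 0.45 v 0.51 | 0.61 v 0.63 | 0.85 v 0.84 | 0.97 v 0.96 |

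Under the null both tests reject at 0.049 to 0.051. An F reference with 41 df (45 − 3 − 1) and no small-sample correction gives 0.052 to 0.055, so the df method should be fixed in advance.

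**Partial follow-up.** Hypothetical: 9 of 45 day-34 values missing completely at random (3 per arm), rho 0.5, 0.8 SD.

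| Analysis | Both visits | Halved | Day 4 only |
|---|---|---|---|
| ANOVA, 36 complete cases | 0.49 | 0.38 | 0.50 |
| Baseline-adjusted, same 36 | 0.64 | 0.46 | 0.50 |
| Baseline-adjusted, all available data | 0.73 | 0.58 | 0.61 |

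Before rounding, adjustment adds about 0.15 / 0.09 / 0.00, and keeping partial data adds a further 0.09 / 0.11 / 0.11.

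**N for 90% power with the joint test at f = 0.25 (equal arms).** At rho 0.5: 36 (both visits), 36 (halved), 45 (day 4 only). At rho 0.3: 36, 42 and 54, where the ANOVA needs 60.

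**The case against.** The planned test is valid, N = 45 is right for it under common assumptions, and nothing in the documents conflicts on this point. At f = 0.25 and rho 0.5 the plan already meets its 0.90 target; adjustment lifts it to between 0.92 and 0.98, and from rho 0.7 upward the two tests barely differ. The larger gains come from a 0.8 SD shift, which the documents do not state and which is smaller than the 1.125 SD implied by the sizing, or from rho 0.3, which is also assumed. All of this stands, and it is why the point is an improvement and not a correction.

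Three further limits stand.

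- The missing-data gains assume loss completely at random. In an assumed scenario with 30% v 10% loss in the worse half of the unseen day-34 values, the mixed model is slightly more biased than the completers' change score (−0.17 v −0.13 SD).
- Baseline adjustment relies on sound randomisation, which the title states but the Procedure section does not describe.
- Missing-data handling is a separate gap that could be closed without changing the model.

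None of these removes the case for using a baseline that is already measured. The title asks about both the short and the medium term, and an effect that lasts to day 34 is where adjustment helps most.

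**Conclusion.** The concern holds as a recommended improvement. The three-time reading is an inference, but a well-supported one. At rho 0.3 to 0.5, the same 45 patients give 0.16 to 0.27 more power for a sustained 0.8 SD effect and 0.12 to 0.18 more for one that halves. At the plan's f = 0.25 and rho 0.5 the gain is 0.01 to 0.07. For a day-4-only effect it runs from 0.06 at rho 0.3 to a loss of 0.01 at rho 0.7 to 0.8. Retaining partial follow-up is worth about 0.1 in the 20% loss example. Confidence in the size is medium, because rho, the shape of the effect and the dropout rate are not in the documents.

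**What to change.** In the SAP, for each main variable:

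1. Analyse day 4 and day 34 with a linear mixed model: group, visit, group × visit, baseline, baseline × visit, unstructured covariance, and a named small-sample df method.
2. Include every randomised patient with at least one follow-up value, in the allocated group.
3. Make the main test the joint 4-df test of no group difference at either visit, and report adjusted pairwise differences with 95% CI at each visit.
4. State that the model assumes missing at random, and that loss depending on unseen day-34 values can still bias it, possibly more than a completers' change score. A sensitivity analysis that shifts missing day-34 values by arm is a useful option, as is a sentence on who is measured at day 34.
5. Restate the sample-size basis: 45 was reproduced for the ANOVA interaction, and at assumed rho 0.5 the new test needs 36 to 45.

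The cost is low: wording, a little more analysis work and no new measurement. The power downside is about 0.01 if the effect is confined to day 4 and rho is high.

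### Uncorrected partial eta squared is labelled by size within each arm: if arms of about 15 are analysed separately, about 23% of arms with no change get a label, nearly always small

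*SAP*

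**What the plan says.** The first paragraph of the Statistical Analysis Plan names one model for the main variables, "an analysis of variance of repeated measures (factorial ANOVA) was applied", and applies it again to the secondary variable. The second paragraph adds a measure of size: "Additionally, the effect size (partial eta squared, η^2) was calculated". It is wanted between groups and also within each group; for the latter, the text is that it "was calculated for the changes produced by comparing within the same intervention group (intragroup". Values are then called small from 0.1, moderate from 0.25 and large above 0.4.

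The SAP does not say how the within-group value is derived from the model. It states no bias correction and no interval for the effect size, and it does not make a label depend on a significant result. The 5% significance level is given separately in the last paragraph.

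The Protocol's Sample size section gives "a sample size of at least 45 patients in total" for three groups and three evaluations. It states neither an allocation ratio nor an allowance for dropout. Under Procedure, the follow-up data come from "clinical variables from the patients who completed the process".

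**The concern.** Partial eta squared is a share of variation and cannot be negative, so chance alone always gives a positive value. In a small arm that value is not trivial compared with a first cut of 0.10. A rule that labels any value from 0.10 upward can therefore describe an arm in which nothing changed as showing an effect.

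What is at stake is how the results read. A taping arm with no change could be reported as having a small effect while its own test is non-significant. The control arm, to which nothing is applied, is open to the same wording. A within-arm change is in any case not a treatment effect, so these labels carry little information even when the change is real.

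**Working it through.** **Inputs.** From the Protocol: 3 groups, 3 visits, N = 45, f = 0.25, alpha 0.05, power 0.90. From the SAP: partial eta squared with cuts at 0.10, 0.25 and 0.40. Assumed: equal arms (45/3 = 15), sphericity and, for the sample size only, a correlation of 0.5 between visits.

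**1. The plan's own figure.** For the group-by-time interaction, df1 = (3−1)(3−1) = 4 and df2 = (45−3)(3−1) = 84. The noncentrality is N·m·f²/(1−ρ) = 45 × 3 × 0.0625/0.5 = 16.875, which gives power 0.911. The smallest adequate N is 44 (power 0.903), or 45 in equal arms. The stated 45 is reproduced.

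**2. One arm with no change, analysed alone.** Here df1 = 2 and df2 = (15−1) × 2 = 28. Partial eta squared = F·df1/(F·df1 + df2), which under the null follows Beta(df1/2, df2/2) = Beta(1, 14).
- Mean: 1/15 = 0.067; the true value is 0.
- P(≥ c) = (1−c)^14, so 0.9^14 = 22.9% are labelled, 0.75^14 = 1.8% reach moderate and 0.6^14 = 0.08% reach large.
- Simulation of 200,000 arms gives 23.0%. Under one non-spherical correlation pattern, 22.4% are labelled and 3.1% reach moderate.
- At least one of three null arms is labelled, per outcome: 1 − (1−0.229)^3 = 54%.
- With dropout, 0.9^13 = 25.4% at 14 per arm and 0.9^11 = 31.4% at 12.

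**3. Label against test.** At df 2, 28, a value of 0.10 means F = (0.10/0.90)(28/2) = 1.56 and p = 0.23. For p = 0.05 the value must reach 1 − 0.05^(1/14) = 0.193. So 22.9 − 5.0 = 17.9 of the 22.9 percentage points are labels on non-significant changes.

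**4. Dependence on the model.** With df1 = 2, P(≥ 0.10) = 0.9^(df2/2).

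| Source of the within-arm value | df | Null arms labelled |
|---|---|---|
| Pooled univariate error | 2, 84 | 0.9^42 = 1.2% |
| Pooled multivariate test | 2, 41 | 0.9^20.5 = 11.5% |
| Separate ANOVA per arm | 2, 28 | 0.9^14 = 22.9% |
| Multivariate test per arm | 2, 13 | 0.9^6.5 = 50.4% |

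**5. Between arms.** The null interaction (df 4, 84) follows Beta(2, 42), with mean 2/44 = 0.045 and P(> 0.10) = 0.9^42 × (1 + 42 × 0.10) = 6.2%. If the between-group value were instead the main effect of group (df 2, 42), the figure would be 0.9^21 = 10.9%.

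**6. Effect of a bias correction, separate ANOVA per arm, same 0.10 cut.**
- Partial epsilon squared, (F−1)df1/(F·df1 + df2), needs F = (0.10 × 28 + 2)/(2 × 0.90) = 2.67. That is a partial eta squared of 0.16, and 0.84^14 = 8.7%.
- One form of partial omega squared, (F−1)df1/((F−1)df1 + 45), needs F = 1 + (0.10/0.90)(45/2) = 3.5. That is a partial eta squared of 0.20, and 0.8^14 = 4.4%.

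**The case against.** The strongest reply is that the 23% rests on a choice the SAP never makes. It names a single factorial model, and simple effects taken from that model with pooled error would mislabel only 1.2% of null arms. This stands: the 23% is conditional. A separate analysis per arm is, however, the most direct reading of a comparison made within one group, and the silence is itself a reason to revise the text.

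The second reply is that the labels are descriptive. They are introduced as an addition, the tests are still read at 5%, and means with SDs are also reported. This stands too. A reader might infer that false-positive conclusions are inflated, but no test or decision rule uses the labels.

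Third, 77% of null arms get no label under the separate-ANOVA reading, and those that do are nearly always called small. That is correct and limits the harm.

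A reader might also infer that the between-arm labels mislead to the same degree, or that moderate and large labels would be common. The first is not supported: at the SAP's own cut the null interaction is labelled in 6.2%. The second needs bands that the SAP does not contain. With assumed cuts of 0.06 and 0.14, for example, 0.94^14 = 42% and 0.86^14 = 12% of null arms would exceed them. Those figures matter only as a warning against lowering the bands while leaving the bias in place.

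**Conclusion.** The point holds in a limited form. As written, the SAP attaches size labels to an upwardly biased statistic in small arms, with no link to the test. With a separate ANOVA in each arm, 15 patients per arm, three visits and sphericity, 23% of null arms are labelled per outcome; 1.8% reach moderate. Across the analyses that the text allows, the rate runs from 1.2% to about 50%, so no single figure can be called the plan's error rate. The randomised comparison, read as the group-by-time interaction, is little affected, and the type I error of the tests is unchanged. The matter is minor: a risk of over-reading within-arm changes that can be removed cheaply.

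**What to change.** 1. Drop the size labels for within-group changes. Report each arm's change as a mean with a 95% CI. This removes the problem whichever model is used.
2. Apply size labels only to the between-arm (group-by-time) effect, using partial omega squared or partial epsilon squared computed from the same F and degrees of freedom. Name the formula, report negative values as zero, and state the bands on the scale of the chosen statistic.
3. Treat an interval for the effect size as optional, since it needs noncentral-F inversion or a bootstrap.

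The cost is a short SAP revision and one line of arithmetic per test, with no new data and no design change. Reported effect sizes will be slightly smaller, and there is a little more analysis work, chiefly if the optional interval is added.
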